7.2 Inclusion criteria

Only subjects meeting all of the following inclusion criteria at the screening (V1) and/or study baseline (V2) visit (as indicated below) will be considered for study enrollment:

Inclusion Criteria	Rationale	Screening	Baseline
1. Written informed consent obtained from the subject.	Administrative	X	
2. Understanding of study procedures and willingness to abide by all procedures during the course of the study.	Administrative	X	
3. Male and female adults (≥ 18 years) suffering from ET as follows: 
 Isolated tremor syndrome with bilateral UL action tremor, At least three years duration before enrollment in the study, With or without tremor in other locations (e.g. head, voice, or lower limbs), Documentation of the diagnosis by a neurologist. 	Efficacy	X	X
4. Following TETRAS Performance subscale criteria as assessed by the investigator: Score of ≥ 2 (at least 1 cm tremor amplitude) in at least two out of three maneuvers of test item 4 (forward outstretched postural tremor, lateral 'wing beating' postural tremor, kinetic tremor). To be confirmed for both ULs separately.	Efficacy	X	X

Inclusion Criteria	Rationale	Screening	Baseline

5. Confirmation of inclusion criterion no. 4 at screening visit V1 by an independent TETRAS expert via video assessment according to the following TETRAS Performance subscale criteria:
 
Score of ≥ 2 (at least 1 cm tremor amplitude) in at least two out of three maneuvers of test item 4 (forward outstretched postural tremor, lateral 'wing beating' postural tremor, kinetic tremor).
 
To be confirmed for both ULs separately.
	Efficacy	X	

6. Fulfilment of all following TETRAS ADL subscale criteria:
 
 • A score of ≥ 1 (slight) in at least five of the items 2 to 9, • A score of ≥ 3 (moderate) in at least two of the items 2 to 9, • A sum score of ≥ 9 in items 2 to 9. 	Efficacy	X	X

7. Ability to perform all four tasks during the kinematic tremor assessment and to complete all assessments of the TETRAS.
	Efficacy	X	X

8. Visible tremor at wrist level in at least one of the four tasks used in the kinematic tremor assessment of the motor dominant UL.
	Efficacy	X	X

9. Clinical need for study treatment of tremor (including mandatory injections in forearm/wrist, elbow, and shoulder muscles) of both ULs (deemed potentially beneficial to the subject by the investigator).
	Efficacy, safety	X	X

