2.3 Other Variables

Other variables are:

- Subject disposition
 - Enrolment (including subjects screened, randomized, treated in Cycle 1, treated in Cycle 2, subjects per analysis set)
 - Study completion/ premature discontinuation of participation (completed Cycle 1/ Cycle 2/ overall, discontinued study in Cycle 1/ Cycle 2/ overall [in total and due to COVID-19 pandemic], with main reason for premature study discontinuation)
 - Visit attendance in Cycle 1 and in Cycle 2 (subjects expected, visit performed, visit not performed, study prematurely discontinued)
- Demographic data and other baseline characteristics (including gender, age [years], age category [18-64 years, 65-84 years, and ≥ 85 years], ethnicity, race, body height [cm], body weight [kg], body mass index [BMI, kg/m²])
- History of ET (age of onset of ET estimated by patient [years], duration since onset of ET (as estimated by patient) [years], family history of ET [yes/no], additional soft neurological signs with ET of uncertain significance [yes/no], motor dominant arm [left/right], tremor on other location(s) than both upper limbs: head [yes/no], face [yes/no], voice [yes/no], lower limb(s) [yes/no], at least one other location [yes/no])
- Previous and concomitant medication
- Previous and concomitant non-drug treatments (procedures)
- Medical history and concomitant diseases
- Timepoint of performance and evaluation of 12-lead ECG
- Injection guidance technique [ultrasound, electromyography, electrical stimulation] by muscle
- Injection cycle length [weeks]
- Total observation period [weeks]

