 - For “Subjects expected at visit”, percentages will be calculated relative to the number of subjects randomized for visits in Cycle 1 and relative to the number of subjects treated in Cycle 2 for visits in Cycle 2.
 - For “Visit performed” and “Visit not performed”, absolute and percent frequencies will be provided. Percentages of columns will be calculated relative to the number of subjects expected at the respective visit.

In case of premature study discontinuation, eCRF question ‘Visit was performed’ will automatically be set to ‘No’ in the eCRF for all visits after premature discontinuation of study participation (except for V11 among subjects in the SES-BP). Therefore, for ‘Visit not performed’ this question will not be used. The number

of subjects with 'Visit not performed' is calculated as number of "Subjects expected at visit" – number of subjects who performed visit.

- For "Study prematurely discontinued", cumulative absolute frequencies will be provided per visit. Absolute frequencies¹⁸ will be determined as numbers of subjects who discontinued study participation before or on the respective visit, but after the preceding visit. For cumulative absolute frequencies, the number of subjects who discontinued the study before or at the respective visit will be displayed.

All performed and all not performed visits until regular study completion or premature study discontinuation (as applicable for the respective subject) will be listed by subject. Flags will also be included for visits performed virtually, visits not performed/ not performed due to COVID-19 pandemic (if applicable).

- Absolute und percent frequencies of subjects excluded from analysis sets will be reported by exclusion reason based on all randomized subjects.
- Demographic data will be summarized descriptively for SES-UP and FAS-UP.

BMI will be calculated as follows:

$$\text{BMI [kg/m}^2\text{]} = \text{weight [kg]} / (\text{height [cm]} * 100)^2 \text{ (rounded to two decimal places)}$$

- Variables on history of ET will be summarized descriptively for SES-UP.

Duration since age of onset of ET [years] will be calculated as age of onset of ET estimated by patient – age as recorded at enrollment, i.e., at Screening (V1)

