4.7.4 Premature discontinuations of study participation

Premature discontinuation of study participation and main reason for discontinuation will be analyzed descriptively (see Section 4.6.1). If premature discontinuation is related to a public health emergency, e.g. due to a COVID-19 outbreak, this information will be documented and listed. Incidence of TEAEs leading to study discontinuation (in total and related to treatment), if any, will be reported as part of the overall summary on TEAEs; details of respective TEAEs will be listed by subject (see Section 4.5.3). Discontinued subjects will generally not be replaced.

For subjects discontinuing the study prematurely and for whom EOS visit V11 was documented,

efficacy endpoints based on TETRAS ADL or TETRAS Performance assessments or kinematic tremor assessment with TremorTek performed at V11 will be analyzed under the study visit which is closest to the recorded V11 date. This will be based on the assessment date relative to study / Cycle 2 baseline, and considering treatment received for each cycle, using adapted visit windows as displayed in [Table 2](#).

Table 2: Adapted Visit Windows for Assignment of V11 to Analysis Visit for subjects prematurely discontinuing the study

| Analysis visit | Window Start Day | Window End Day | Window(s) applicable for |
|----------------|------------------|------------------------|--|
| Week 4 (V3) | 2 | 35 | all subjects ¹ |
| Week 6 (V4) | 36 | 49 | |
| Week 8 (V5) | 50 | 70 | |
| Week 12 (V6) | 71 | 105 | |
| Week 18 (V7) | 108 | 147 | |
| Week 24 (V8) | 148 | Open end | subjects ¹ not treated in Cycle 2 |
| Week 24 (V8) | 148 | Day of treatment in C2 | subjects ¹ treated in Cycle 2 |
| Week 4 (V9) | C2 / Day 2 | C2 / Day 35 | |
| Week 6 (V10) | C2 / Day 36 | C2 / Day 63 | |
| Week 12 (V11) | C2 / Day 64 | Open end | |

¹ subjects prematurely discontinuing the study

Note that V11 EOS data will never be assigned to any (cycle) baseline visit based on the above rules.

In general, if based on the above windows, a V11 EOS assessment would be assigned to a timepoint for which a regular visit was performed and respective TETRAS ADL/ TETRAS Performance / kinematic tremor assessments are available, then the respective data from the regularly performed visit will be used for analysis, and V11 data will only be listed.

All other data collected at EOS visit (V11) will generally be analyzed at V11.

5 Sample Size Determination

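### Three SAP derivation rules are wrong as written (ET duration has reversed sign, BMI rounds to 0.00, Days 106–107 fall in no visit window), affecting descriptive outputs only

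*SAP*

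**What the plan says.** **(a) Duration of ET.** SAP 2.3 lists the variable as "duration since onset of ET (as estimated by patient) [years", in years. SAP 4.6.1 then states that it "will be calculated as age of onset of ET estimated by patient", from which the age at enrolment is subtracted. The full phrase shows the order of the terms: it "will be calculated as age of onset of ET estimated by patient – age as recorded at enrollment, i.e., at Screening (V1").

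**(b) BMI.** SAP 4.6.1 divides weight in kg by a squared denominator that reads "height [cm]} * 100)^2" in the machine-read text (the brace is a typesetting remnant). The result is labelled kg/m² and is to be "rounded to two decimal places". SAP 2.3 gives height in cm and weight in kg. BMI is a baseline characteristic (SAP 2.3) and a safety time-course variable with changes from study baseline (SAP 2.2.2.3 and 4.5.3).

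**(c) Windows for early-termination data.** For subjects who stop early, SAP 4.7.4 assigns TETRAS and TremorTek data from the end-of-study visit (V11) to the scheduled visit nearest in time, using the windows in Table 2. Two adjacent rows read "Week 12 (V6) | 71 | 105" and "Week 18 (V7) | 108 | 147".

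SAP Section 6, which lists the changes from the protocol, mentions none of these rules.

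**The concern.** These are operative rules. SAP 1.1 says that the document is meant to guide statistical programming. A programmer who follows (a) and (b) literally produces wrong baseline and safety tables. One who silently corrects them departs from the SAP without a record.

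Rule (c) is different in kind. It yields no value rather than a wrong one, and the table disagrees with the sentence that it is meant to implement. It is also the least visible of the three. A negative duration or a BMI of zero stands out in any output; an efficacy record that matches no window may not. If the gap were noticed only after unblinding, the assignment would have to be settled then, even though the closest-visit sentence already gives the answer.

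**Working it through.** **Windows (the plan's own figures).** Inputs are the nominal Cycle 1 study days in Protocol Table 5 (28, 42, 56, 84, 126, 168) and the windows in SAP Table 2. Rule tested: each window ends at the midpoint between its nominal day and the next, and the following window starts one day later.

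| Visit | Nominal day | Table 2 start | Table 2 end | Midpoint with next visit | Start implied by previous end + 1 |
|---|---|---|---|---|---|
| V3 | 28 | 2 | 35 | (28+42)/2 = 35 | – |
| V4 | 42 | 36 | 49 | (42+56)/2 = 49 | 36 |
| V5 | 56 | 50 | 70 | (56+84)/2 = 70 | 50 |
| V6 | 84 | 71 | 105 | (84+126)/2 = 105 | 71 |
| V7 | 126 | **108** | 147 | (126+168)/2 = 147 | **106** |
| V8 | 168 | 148 | open, or day of Cycle 2 treatment | – | 148 |

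All five end days reproduce, and so do all the implied start days except V7. From Day 2 onward, the uncovered days are exactly 106 and 107. In Cycle 2 (Weeks 4, 6 and 12, that is Days 28, 42 and 84) the midpoints are 35 and 63. Table 2 matches both and has no gap.

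The closest-visit rule applied to the two uncovered days:
- Day 106: 106 − 84 = 22 days from V6; 126 − 106 = 20 days from V7.
- Day 107: 107 − 84 = 23 days from V6; 126 − 107 = 19 days from V7.

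Both go to V7. The protocol's ±7-day scheduling windows (V6 Days 77–91, V7 Days 119–133) do not explain a start on Day 108 either.

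**ET duration.** As written: onset age − age at Screening. Intended: age at Screening − onset age. The ages below are illustrative.

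| Onset age | Age at Screening | As written | Intended |
|---|---|---|---|
| 62 | 65 | −3 | 3 |
| 45 | 65 | −20 | 20 |
| 20 | 70 | −50 | 50 |

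The magnitude is right and the sign is reversed. Onset cannot come after screening, so the written value is never positive. Inclusion criterion 3 (Protocol 7.2) asks for "At least three years duration before enrollment in the study". If the patient's estimate agrees with that, written values will be about −3 or lower.

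**BMI.** As written: w / (h × 100)², with h in cm. Intended: w / (h / 100)². The ratio of intended to written is (h × 100)² / (h / 100)² = 100⁴ = 10^8 at any height. The weights and heights below are illustrative.

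| Weight, height | As written | Rounded | Intended |
|---|---|---|---|
| 50 kg, 150 cm | 50 / 15,000² = 2.2 × 10⁻⁷ | 0.00 | 22.22 |
| 80 kg, 175 cm | 80 / 17,500² = 2.6 × 10⁻⁷ | 0.00 | 26.12 |
| 120 kg, 190 cm | 120 / 19,000² = 3.3 × 10⁻⁷ | 0.00 | 33.24 |

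To round to anything above 0.00, the written value would have to reach 0.005, which needs a true BMI of 0.005 × 10^8 = 500,000. Every subject therefore gets 0.00, and so does every change from baseline.

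**The case against.** The strongest reply is that these are slips whose intended meaning is plain. The variable name, the kg/m² label and the closest-visit sentence each show what was meant. SAP 1.1 also provides for quality control of datasets and outputs, and a negative duration or zero BMI would be caught there. This stands as to likelihood: a BMI table of zeros is not a plausible final result. It does not make the written rules correct, and a correction made only in code leaves no record in the SAP.

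A second reply is that the SAP text was read from PDF by a program. The BMI operator comes from a typeset formula, and 108 differs from 106 by one similar-looking digit. This stands in part: if the original shows a division or 106, the corresponding item falls away. The ET duration rule is plain prose and is not open to this doubt.

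Three stronger readings are tempting, and the documents do not support them:
- **That the duration figure bears on eligibility.** Inclusion criterion 3 is checked by the site at Screening and baseline and calls for a neurologist's documentation of the diagnosis. The SAP variable uses the patient's own estimate and is only summarised. The SAP (24 January 2024) also post-dates the data review meeting of 17 January 2024, so it could not have influenced entry.
- **That assessments on Days 106–107 are dropped from the efficacy time course.** No passage says so. SAP 4.7.4 restricts V11 data to a listing where a regular visit already supplies that timepoint, not because of a gap. The data are unassigned by the table and assigned to V7 by the prose.
- **That the efficacy conclusions are at risk.** The Week 6 (V4) window, Days 36–49, joins its neighbours without a gap. Week 12 and Week 18 values belong to the other efficacy endpoints, which SAP 4.1.3 analyses descriptively. SAP 4.1.2.1 reports the key secondary endpoints as complete for all treated subjects.

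**Conclusion.** The point holds as a correction to descriptive derivations. Followed literally, SAP 4.6.1 gives a reversed sign for ET duration in every subject with onset before the screening age, and a BMI of 0.00 for everyone. SAP Table 2 leaves two days, 106 and 107, without an analysis visit, contrary to its own closest-visit rule. No primary or key secondary Week 6 result and no eligibility decision changes.

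The window gap matters only if a subject stopped early in Cycle 1 with V11 efficacy data on one of those two days; the documents do not show whether any did. Items (b) and (c) assume that the operator and the digit were read correctly from the PDF.

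**What to change.** Check the BMI operator and the Week 18 start day once against the original PDF. Then make three edits to the SAP:

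1. SAP 4.6.1: duration since onset [years] = age at Screening (V1) − patient-estimated age at onset.
2. SAP 4.6.1: BMI [kg/m²] = weight [kg] / (height [cm] / 100)².
3. SAP 4.7.4, Table 2: start the Week 18 (V7) window on Day 106.

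Check that the analysis dataset specification and programs, which are not among the documents reviewed, follow the corrected rules. Under Protocol Section 12, changes made before database close or unblinding go into an amendment, and all alterations are summarised in the clinical study report. If the SAP can no longer be amended, record the three corrections there. The cost is three line edits and a check of the code, with no effect on design, sample size or inference.

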4.6.2 Other Data

Important PDs and final reasons for exclusion of subjects from analysis sets were determined in the data review meeting (DRM) performed on 17Jan2024 prior to database close and unblinding. Classified important PDs as well as classified reasons for exclusion of subjects from analysis sets will be analyzed by absolute and percent frequencies over all randomized subjects.

Important PDs and reasons for exclusions from any analysis sets will be displayed in separate by subject listings, displaying the respective class of PD/exclusion reasons and further details. The listing of important PDs will also display information on relatedness to COVID-19 pandemic [yes/no] and the assessment as major or minor according to decisions made during the blind data review meeting (statistical judgement).

To describe the impact of COVID-19 pandemic on study conduct, an additional listing will display all (important or non-important) PDs and other events related to COVID-19 pandemic not considered as PDs (including, e.g., premature discontinuations due to COVID-19 pandemic and visits performed virtually due to COVID-19 pandemic).

4.6.3 Subgroup Analyses

Treatment effects by pooled study site will be analyzed for the primary and the two key secondary efficacy endpoints by use of an ANCOVA model with a treatment-by-pooled site interaction term. The respective analyses are specified as exploratory sensitivity analyses (see Section 4.1.1.2 for the primary efficacy endpoint, and Section 4.1.2.1 for the two key secondary efficacy endpoints). No further subgroup analyses are planned for this study.

4.7 Special Statistical / Analytical Issues

4.7.1 Interim Analyses

No interim analysis will be performed in this study.

4.7.2 Multiplicity Adjustment

[REDACTED]

4.7.3 Pooling of Sites

In case of convergence issues in ANCOVA models, study sites might be pooled for statistical analysis. During the data review meeting performed on 17Jan2024 under double blind conditions, pooling of study sites was only considered necessary for sensitivity analysis no. 2 of the primary and the two key secondary efficacy endpoints (see Sections 4.1.1.2 and 4.1.2.1 for details). No need for further pooling was seen during the DRM.

4.7.4 Premature discontinuations of study participation

Premature discontinuation of study participation and main reason for discontinuation will be analyzed descriptively (see Section 4.6.1). If premature discontinuation is related to a public health emergency, e.g. due to a COVID-19 outbreak, this information will be documented and listed. Incidence of TEAEs leading to study discontinuation (in total and related to treatment), if any, will be reported as part of the overall summary on TEAEs; details of respective TEAEs will be listed by subject (see Section 4.5.3). Discontinued subjects will generally not be replaced.

For subjects discontinuing the study prematurely and for whom EOS visit V11 was documented,

efficacy endpoints based on TETRAS ADL or TETRAS Performance assessments or kinematic tremor assessment with TremorTek performed at V11 will be analyzed under the study visit which is closest to the recorded V11 date. This will be based on the assessment date relative to study / Cycle 2 baseline, and considering treatment received for each cycle, using adapted visit windows as displayed in [Table 2](#).

Table 2: Adapted Visit Windows for Assignment of V11 to Analysis Visit for subjects prematurely discontinuing the study

| Analysis visit | Window Start Day | Window End Day | Window(s) applicable for |
|----------------|------------------|------------------------|--|
| Week 4 (V3) | 2 | 35 | all subjects ¹ |
| Week 6 (V4) | 36 | 49 | |
| Week 8 (V5) | 50 | 70 | |
| Week 12 (V6) | 71 | 105 | |
| Week 18 (V7) | 108 | 147 | |
| Week 24 (V8) | 148 | Open end | subjects ¹ not treated in Cycle 2 |
| Week 24 (V8) | 148 | Day of treatment in C2 | subjects ¹ treated in Cycle 2 |
| Week 4 (V9) | C2 / Day 2 | C2 / Day 35 | |
| Week 6 (V10) | C2 / Day 36 | C2 / Day 63 | |
| Week 12 (V11) | C2 / Day 64 | Open end | |

¹ subjects prematurely discontinuing the study

Note that V11 EOS data will never be assigned to any (cycle) baseline visit based on the above rules.

In general, if based on the above windows, a V11 EOS assessment would be assigned to a timepoint for which a regular visit was performed and respective TETRAS ADL/ TETRAS Performance / kinematic tremor assessments are available, then the respective data from the regularly performed visit will be used for analysis, and V11 data will only be listed.

All other data collected at EOS visit (V11) will generally be analyzed at V11.

5 Sample Size Determination

The results of a previous study [4] suggest that a treatment effect of about one standard deviation might be expected. For a 5% type I error and a randomization ratio of 2:1 a total sample size of 51 analyzable subjects is required to achieve 90% power. In order to account for uncertainty in parameter estimates and drop-outs it has been decided to randomize approximately 75 subjects.

6 Changes in the Planned Analyses

Compared to CSP version 3.0 dated 31-May-2021 and amendment 1 to CSP version 3.0 dated 26-MAY-2023, the following change to planned analyses is included in this SAP:

Sections [2.2.1.2.2](#) and [2.2.1.3](#):

- For precision, “as assessed by the investigator” was added to the definition of all other secondary endpoints and all other efficacy endpoints that are based on the TETRAS performance assessments in the bilateral treatment period. In accordance with the CSP, the IRP did not perform any assessments in Cycle 2.

Section [2.2.1.3](#):

- In the definition of other efficacy endpoints for the bilateral treatment period (Cycle 2) based on angular tremor amplitude assessments, the word “difference” was missing in the CSP and therefore added in part c) of the definition before “between both ULs”.
- The following restriction was added to definition of other efficacy endpoints for the bilateral treatment period (Cycle 2) based on angular tremor amplitude assessments:
“Changes from study baseline are only analyzed for motor-dominant UL because, in accordance with the visit schedules for treatment Cycles 1 and 2 in the CSP (see Tables 5 and 6), angular tremor amplitude of motor-dominant UL was only assessed in Cycle 2.”

Section 3:

- In the definition of the FAS-UP, “study baseline (V2)” was changed to “study baseline” and in the definition of the FAS-BP, “Cycle 2 baseline visit (V8)” was changed to “Cycle 2 baseline”.
References to the study baseline and the Cycle 2 baseline definition in Section 4 were inserted. These changes were made to ensure consistency of definitions of FAS-UP and FAS-BP with definition of efficacy endpoints specified as changes from at study baseline or changes from Cycle 2 baseline as defined in Section 4 and to avoid unnecessary removal of subjects from these two analysis sets. E.g., the change of the FAS-UP definition implies that a subject who does not have any scores of tremor amplitude at wrist level at study baseline visit (V2) and would thus be removed from the FAS-UP according to the FAS-UP definition in the CSP, will actually be included in the FAS-UP if he/she has at least one score of tremor amplitude at wrist level at screening visit (V1).
- For consistency, “injected UL” was changed to “injected motor-dominant UL” in the definition of the FAS-UP. This is in accordance with the specification in CSP Section 8.1.1 that the motor-dominant UL is to be injected in the unilateral treatment period (Cycle 1), the specification in CSP Section 9.1.1.2.1 that angular tremor amplitude (for evaluation of the primary efficacy endpoint and some other efficacy endpoints) is to be performed “for the injected UL(s), i.e., the motor-dominant UL in the unilateral and both ULs in the bilateral treatment period” and the specification of the unilateral key secondary efficacy endpoint in Section 12.3.1.2.1 (“Change from study baseline to Week 6 in TETRAS Performance dominant UL Score [...] in the unilateral treatment period as assessed by the investigator.”).

Sections 4.1.1.2 & 4.1.2.1:

- For sake of preciseness, “among all treated subjects” was added after “In case more than 10% missingness on the primary efficacy endpoint occurs in either treatment group” in the specification of the condition when sensitivity analysis no 4 (based on multiple imputation) needs to be performed for the primary efficacy endpoint (Section 4.1.1.2).
- Likewise, “among all treated subjects” was added after “in case of more than 10% missingness on the respective key secondary endpoint” regarding to need to perform respective sensitivity analysis for key secondary endpoints (Section 4.1.2.1).

7 References

[1]

[REDACTED]

[2] Elble RJ. The Essential Tremor Rating Assessment Scale. Journal of Neurology & Neuromedicine. 2016;1(4):34-8.

[3]

